16.2 Secondary Endpoint Analyses

The Secondary endpoints for dose escalation are:

- Number, severity, and duration of TEAEs according to the NCI-Common Terminology Criteria for Adverse Events (CTCAE) v4.0.
- Number, severity, and duration of treatment-related AEs according to NCI-CTCAE v4.0.
- PK profile.
- irBOR and BOR according to modified irRC and to RECIST 1.1, respectively, per investigator assessment.
- Pharmacodynamic profile.
- Serum titers of anti-avelumab antibodies.

TEAE related endpoints will be discussed in the [Section 17.1](#). Other secondary endpoints such as cytokine profile, receptor occupancy, PK profile, immunogenicity will be addressed in [Sections 16.3, 16.4, 16.5, or 16.6](#), respectively. No efficacy summary will be performed due to small sample size and heterogeneous population in dose escalation part, but the endpoints at subject level will be derived as described in this section and displayed in the listings.

Efficacy evaluations include lesion assessments for target, non-target, and new lesions, tumor response according to RECIST 1.1 (1) and irRC (2). The confirmed BOR is defined as the best response obtained among all tumor assessment visits after first dose of study treatment until documented disease progression, taking into account the following requirements for confirmation:

- CR or PR needs to be confirmed at a subsequent tumor assessment, preferably at the regularly scheduled 6-week assessment interval, but no sooner than 4 weeks after the initial documentation of CR or PR.
- PR can be confirmed at an assessment later than the next assessment after the initial documentation of PR.

- The minimum duration for a BOR of SD is defined as at least 37 days after start of study treatment accounting for permitted deviations from the tumor assessment visit schedule.

Table 2 summarized the derivation rules for the BOR when confirmation from subsequent assessment is needed (1). It is reasonable to consider a subject with time point response of PR-SD-PR, PR-NE-PR or CR-NE-CR as a confirmed response as long as the second CR or PR is at least 28 days away from the first time point.

Table 2 Best Overall Response when Confirmation of CR/PR Required

Initial overall response	Subsequent overall response	Confirmed time point overall response
CR	CR	CR provided subsequent CR is ≥ 28 days away from the first time point
CR	PR	SD provided minimum criteria for SD duration met; otherwise, PD
CR	SD	SD provided minimum criteria for SD duration met; otherwise, PD
CR	PD	SD provided minimum criteria for SD duration met; otherwise, PD
CR	NE	SD provided minimum criteria for SD duration met, otherwise, NE
PR	CR	PR provided subsequent CR is ≥ 28 days away from the first time point
PR	PR	PR provided subsequent PR is ≥ 28 days away from the first time point
PR	SD	SD
PR	PD	SD provided minimum criteria for SD duration met, otherwise, PD
PR	NE	SD provided minimum criteria for SD duration met, otherwise, NE
SD	Any	SD provided minimum criteria for SD duration met, otherwise, NE
PD	Any	PD
NE	NE	NE

CR = complete response, PR = partial response, SD = stable disease, PD = progressive disease, and NE = Not assessable.
 If a subject only has a response value of NE or the only response value is SD and is within 36 days of the first dose date, the best response will be NE.

For irBOR, immune-related complete response (irCR), immune-related partial response (irPR), and irPD need to be confirmed by a second, consecutive assessment at least 4 weeks apart as described in Table 3 (1, 2). It is reasonable to consider a subject with time point response of irPR-irSD-irPR, irPR-NE-irPR or irCR-NE-irCR as a confirmed response as long as the second irCR or irPR is at least 28 days away from the first time point. irPD is also considered to be confirmed if the following event occurs:

- If subject is assessed with time point response of irPD-NE-irPD as long as the second irPD is at least 28 days away from the first time point; or
- If subject dies within 84 days after the initial observation of irPD; or

- If subject receives subsequent anti-cancer drug therapy within 84 days after the initial observation of irPD; or
- If subject experiences clinical deterioration as assessed by investigator and recorded as reason for treatment discontinuation prior to or within 84 days after the assessment of irPD.

In case a subject with a confirmed CR relapses within 1 year after stopping treatment, one re-initiation of treatment is allowed according to Protocol. If the subject has irPD assessed at the same visit as the PD prior to the initiation of treatment, the irPD will be considered as confirmed. The minimum duration of immune-related stable disease (irSD) is defined as at least 37 days from Day 1.

Table 3 Immune-related BOR when Confirmation of irCR, irPR, irPD Required

Initial overall response	Subsequent overall response	Confirmed time point overall response
irCR	irCR	irCR provided subsequent irCR is ≥ 28 days away from the first time point
irCR	irPR	irSD provided minimum criteria for irSD duration met; otherwise, irPD
irCR	irSD	irSD provided minimum criteria for irSD duration met; otherwise, irPD
irCR	irPD	irSD provided minimum criteria for irSD duration met; otherwise, irPD
irCR	NE	irSD provided minimum criteria for irSD duration met, otherwise, NE
irPR	irCR	irPR provided subsequent irCR is ≥ 28 days away from the first time point
irPR	irPR	irPR provided subsequent irPR is ≥ 28 days away from the first time point
irPR	irSD	irSD
irPR	irPD	irSD provided minimum criteria for irSD duration met, otherwise, irPD
irPR	NE	irSD provided minimum criteria for irSD duration met, otherwise, NE
irSD	Any	irSD provided minimum criteria for irSD duration met, otherwise, NE
irPD	irPD	irPD provided subsequent irPD is ≥ 28 days away from the first time point, death or take subsequent anti-cancer drug therapy within 84 days after the first time point, or clinical deterioration.
irPD	Missing	irPD if subject dies or takes subsequent anti-cancer drug therapy within 84 days after the initial observation of irPD, or clinical deterioration, otherwise, NE
NE	NE	NE

irCR = immune-related complete response, irPR = immune-related partial response, irSD = immune-related stable disease, irPD = immune-related progressive disease, and NE = Not evaluable.

If a subject only has a response value of NE or the only response value is irSD and is within 36 days of the first dose date, the best response will be NE

These evaluations will be presented in data listings with detailed information, such as lesion type, site, size, time point tumor response by type collected per eCRF pages as well as BOR and irBOR, for all the subjects from SAF analysis set.

16.3 Cytokine Profile

The following parameters are assessed for the cytokines profile based on SAF analysis set:

-
- Rantes, Interleukin-17, IL-6, MCP-1, IL-1beta, IL-2, IL-4, IL-5, IL-10, IL-12p70, IL-13, TNF-Alpha, IFN-Gamma.

These parameters will be summarized by visit and dose level using the following variables:

- Absolute value
- Log fold change from baseline

If values are indicated to be below the lower limit of quantification (LLOQ), they will be imputed as 0.5* LLOQ for summary analysis. If multiple measurements per time point per subject exist, a single signal value will be derived by averaging.

Log fold change from baseline (logFC) is defined as

- $\text{logFC (cytokine at time } t) = \text{log}(\text{cytokine signal at time } t) - \text{log}(\text{cytokine signal at baseline})$:

The cytokine data will be displayed graphically by dose level for each parameter:

- Boxplot of absolute value by visit (logarithmic and raw scale)
- Boxplot of log fold change from baseline by visit
- Line plot of per-subject data

The cytokine listing will be produced with relevant variables such as dose level, subject identifier, visit, parameter names and results.

16.4 Receptor Occupancy

The receptor occupancy was assessed by flow cytometry on PBMC (peripheral blood mononuclear cell) samples collected on Day 1 before start of the infusion, at 4 and 48 hrs after the start of infusion, and before the start of each infusion on Days 15, 29, 43, and 85, if applicable. Quality of PBMCs such as cell viability was determined after thawing, $\geq 85\%$ cell viability is required for reliable receptor occupancy assessment. Additional or alternative criteria might be used if a review of the data indicates that this is necessary. Data generated from samples with inadequate quality will be excluded from the analysis.

This data will be summarized using descriptive statistics (n, mean, standard deviation, etc.) by visit and by dose level and overall based on SAF analysis set. Line plots will be created to display the data graphically across visit per subject by dose level, or to display the mean and standard deviation across visit by dose level.

A listing of receptor occupancy will include variables such as subject identifier, visit, date of assessment, test parameter, and values etc.

16.5 Pharmacokinetic Profile

16.5.1 Missing PK Data

All PK analyses will be based on the PK analysis set.

- **Concentrations below the limit of assay quantitation**

PK concentrations below LLOQ are taken as zero for descriptive statistics.

PK concentrations below LLOQ, which are before the last quantifiable data point, will be taken as zero for calculating the AUC of single dose profiles. Concentration below LLOQ, which occur after the last quantifiable data point, will not be considered in the calculation of the terminal first order rate constant (λ_z).

- **Deviations, missing concentrations and anomalous values**

Concentrations will be set to missing in summary tables if the value is reported as no result.

If a PK parameter cannot be derived from a subject's concentration data, the parameter will be coded as NC (not calculated). (Note that NC values will not be generated beyond the day that a subject discontinues the treatment). For statistical analyses (i.e. analysis of variance), PK parameters coded as NC will be set to missing.

If an individual subject has a known biased estimate of a PK parameter (due for example to a deviation from the assigned dose level), this subject/value will be excluded from the descriptive statistics and instead the result will be listed in a separate table.

Relevant decisions on subject inclusion in the PK analysis set will be made before database lock in the Database Review Meeting (DRM).

16.5.2 Descriptive PK Analysis

Avelumab concentrations in serum will be displayed in listing and descriptively summarized by treatment, cohort, day and nominal time using the number of non-missing observations, number of missing observations, arithmetic mean, standard deviation, coefficient of variation (CV%), standard error of the mean (SEM), minimum, median and maximum. The pre-dose samples will be considered as if they had been taken simultaneously with the administration. Additional tables listing trough concentrations (Cmin) per cohort/day/administration will also be provided, and summarized descriptively using the aforementioned statistics.

Descriptive statistics of PK parameters will additionally show the geometric mean (GeoMean), the geometric coefficient of variation (GeoCV) and the 95% confidence interval for the GeoMean.

For the calculation of descriptive statistics, values as presented in the data listings will be used. Minimum and maximum will be presented to the same decimal precision as collected. Mean, median and GeoMean will be presented to one decimal place more than the precision of the data collected. SD and SEM will be presented to two decimal places more than the precision of the data collected. The coefficient of variation (CV%), GeoCV and the 95% CI will be reported to 1 decimal place.

16.5.3 Pharmacokinetic Non-Compartment Analysis

Pharmacokinetic parameters for avelumab will be evaluated according to standard non-compartmental analysis (NCA) by the PK/pharmacodynamic data processing group of QPD, Merck Serono, Darmstadt, Germany, using the validated software tool Phoenix®/WinNonlin 6.3® (or later).

The PK parameters listed below will be calculated for avelumab using the actual time elapsed from dosing (or using scheduled time if actual time is not available).

C _{max}	Maximum observed concentration in serum
t _{max}	Time to reach C _{max}
AUC _{0-t}	Area under the serum concentration-time curve from time zero to the last quantifiable concentration
C _{min}	The minimum observed concentration during a complete dosing interval (serum trough concentration)

When applicable the following parameters will also be calculated:

AUC _{0-∞}	Area under the serum concentration-time curve from time zero extrapolated to infinity. $AUC_{0-\infty} = AUC_{0-t} + AUC_{extra}$, where $AUC_{extra} = C_{last\ pred} / \lambda_z$
AUC _{extra}	The AUC from time t _{last} extrapolated to infinity given as a percentage of AUC _{0-∞}
t _{1/2}	Apparent terminal half-life, calculated by $\ln 2 / \lambda_z$
λ_z	Apparent terminal elimination rate constant determined by log-linear regression analysis of the measured serum concentrations of the terminal log-linear phase.
CL	Apparent total body clearance of drug from serum. $CL = Dose\ i.v. / AUC_{0-\infty}$
V _z	Apparent volume of distribution during terminal phase. $V_z = Dose / (AUC_{0-\infty} * \lambda_z)$
AUC _{0-t} /Dose	Dose-Normalized AUC _{0-t} . Normalized using actual dose.
C _{max} /Dose	Dose-Normalized C _{max} , Normalized using actual dose.

The following PK parameters will be calculated for diagnostic purposes and listed, but will not be summarized:

- The time interval (h) of the log-linear regression to determine λ_z (t_{1/2}, Interval).
- Number of data points (t_{1/2}, N) included in the log-linear regression analysis to determine λ_z .
- Goodness of fit statistic (Rsq) for calculation of λ_z .
- Percentage of AUC_{0-∞} obtained by extrapolation (%AUC_{extra}), calculated by $(1 - [AUC_{0-t}/AUC_{0-\infty}]) \times 100$. If %AUC_{extra} is greater than 20%, AUC_{0-∞}, CL/f, and V_z/f will be included in the Phoenix® WinNonlin® parameter outputs but will be flagged.

The regression analysis (determination of λ_z) should contain as many data points as possible (but excluding C_{max}) and has to include concentration data from at least 3 different time points, consistent with the assessment of a straight line (the terminal elimination phase) on the log-transformed scale. The observation period over which the regression line is estimated should be at least twofold the resulting t_{1/2} itself.

The calculation of the AUCs will be performed using the mixed log-linear trapezoidal method (linear up, log down). Extrapolated areas will always be computed using the predicted last

concentration that is estimated using the linear regression from terminal rate constant determination.

If $AUC_{extra} > 20\%$ then $AUC_{0-\infty}$ and all related parameters will be excluded from descriptive statistics.

16.5.4 Figures

Individual serum concentration-time profiles (linear and semi-logarithmic scales) will be plotted by dose level. Mean serum concentrations per administration will also be plotted on linear ($\pm SD$) and semi-logarithmic scales using schedule time points.

Dose proportionality will be evaluated for avelumab using data from subjects with a full PK profile, and will be presented graphically as follows:

- Boxplots of dose-normalized PK parameters ($AUC_{0-t}/Dose$, $AUC_{0-\infty}/Dose$ and $C_{max}/Dose$) by dose level.
- Scatterplots with regression lines for individual AUC_{0-t} , $AUC_{0-\infty}$ and C_{max} values (where applicable) and dose normalized AUC_{0-t} , $AUC_{0-\infty}$ and C_{max} versus dose on a linear scale.

CCI

CCI

17 Safety Evaluation

The subsections in this section include specifications for summarizing safety endpoints that are common across clinical trials such as adverse events, laboratory tests and vital signs.

All safety analyses will be performed using the SAF analysis set, unless otherwise specified.

All safety parameters will be summarized by dose level and overall, unless otherwise stated.

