3.3 Pharmacokinetics / Immunogenicity Findings

Preliminary PK assessments have been collected and analyzed in the current ongoing EMR100070-001 trial. The preliminary results based on the data available as of 19 December 2014 are presented under the individual trial headings.

Pharmacokinetics following the first 1-hour infusion and dose proportionality of avelumab have been characterized in 57 Caucasian subjects treated in the dose escalation and expansion cohort of the Phase I Trial EMR100070-001 by standard non-compartmental analysis based on rich serum concentration-time data obtained over a complete dosing interval of 2 weeks (= tau). The analysis of these data revealed that the exposure parameters maximum concentration observed post-dose (C_{max}) and area under the concentration-time curve (AUC_{tau}) increased with the doses in a linear fashion.

The apparent terminal half-life ($t_{1/2}$) was 69 hours (mean) \pm 21 hours (standard deviation) for 1 mg/kg, 84 ± 22 hours for the 3 mg/kg, 106 ± 29 hours for 10 mg/kg, and 134 ± 74 hours for the 20 mg/kg dose. Taking into account the variability, the $t_{1/2}$ of the 10 and 20 mg/kg doses can be regarded as similar, indicating that target mediated elimination does not increase at these doses. This implies that target occupancy is likely to be high at these 2 doses throughout the dosing interval.

Trough concentrations (C_{min}) were obtained for the majority of subjects enrolled in the trial. The median C_{min} at the end of the first cycle after administration of the 10 mg/kg dose was 20 μ g/mL

(n=256). This median C_{min} increased during the subsequent cycles to 24 $\mu\text{g/mL}$ (second cycle; n=233), 26 $\mu\text{g/mL}$ (third cycle; n=167), and remained between 24 and 37 $\mu\text{g/mL}$ during the subsequent cycles (n=22 to 114) indicative for no significant accumulation with the biweekly dosing scheme. Median C_{min} after the 3 mg/kg dose were 3.7 $\mu\text{g/mL}$ after the first dose, 3.9 $\mu\text{g/mL}$ after the second dose and 8.3 $\mu\text{g/mL}$ after the third dose (n=7 to 12), though some trough values below 1 $\mu\text{g/mL}$ were observed, as well as antidrug antibodies in at least 1 subject in this dose group on Day 85 of the treatment period, accompanied by loss of quantifiable exposure. Median trough concentrations after the 20 mg/kg dose were 44, 70, and 77 $\mu\text{g/mL}$ after the first, second, and third dose, respectively (n=14 to 19).

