3.4.1 Clinical Pharmacodynamics

Receptor occupancy was measured in vitro by flow cytometry on peripheral blood CD3+ T-cells after spiking of human whole blood samples from 8 healthy volunteers with avelumab over a concentration range of 0.003 to 10 µg/mL. In this assay, free receptors were measured in samples spiked over this range and compared with the amount of free receptors in the unspiked sample. A 50% receptor occupancy was observed at a drug concentration of 0.122 µg/mL ± 0.042 µg/mL (standard deviation) and a plateau indicating at least 95% receptor occupancy was reached in all donor blood samples at 1 µg/mL.

These in vitro data combined with PK data were confirmed in ex-vivo samples taken at C_{min} after the first dose (Day 15) in a small number of subjects during the initial dose escalation part of the Phase Ib Trial EMR100070-001 (n=9). For doses of 10 mg/kg, target occupancy (TO) was greater than 90% for these 4 subjects, at trough serum levels ranging between 12.69 to 26.87 µg/mL. Also, for doses of 3 mg/kg, available TO data for 2 subjects with trough levels ranging from 4.56 to 6.99 µg/mL, showed greater than 90% TO at trough exposure levels. At dose level 1 mg/kg, 2 out of 3 subjects displayed less than 90% TO at trough serum concentrations. Avelumab serum concentrations were below the quantification limit of 0.2 µg/mL in these 2 subjects.

Based on the observed avelumab serum concentrations in the EMR100070-001 Phase I clinical trial and the in vitro receptor occupancy data, trough concentrations were sufficient to achieve full target occupancy throughout the entire dosing interval in all of the subjects receiving the 10 mg/kg dose. After the 3 mg/kg dose, C_{min} were insufficient in 3 of the 13 subjects to assure full target occupancy; therefore, in order to achieve target saturation during the whole treatment period in all subjects, the dose of 10 mg/kg every 2 weeks was selected as the dose for further investigation in the Phase Ib expansion cohorts and for the subsequent clinical studies.

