7.5 Pharmacokinetics

7.5.1 Dose Escalation Phase

Pharmacokinetic parameters include AUC_{0-t} , $AUC_{0-\infty}$, λ_z , C_{max} , t_{max} , and $t_{1/2}$ (for definitions, see Section 8.5.3.2). Blood samples for the analysis of serum concentrations of avelumab will be drawn in all subjects according to the schedule listed below and the Schedule of Assessments (see [Appendix I](#)).

- Day 1: prior to and at the end of the 1-hour infusion, and at 0.5, 1, 2, 4, 6, and 12 hours after infusion.
- Day 2: 24 and 36 hours after infusion (optional).
- Day 3: 48 hours after infusion (± 6 hours) (optional).
- Days 15, 29, 43, 85, 127, and 169: prior to infusion (trough value) and immediately after infusion is completed (peak value).

- For the 10 mg/kg of avelumab once weekly cohort, blood samples for PK determinations will be collected from all subjects within 2 hours prior to each infusion at Weeks 1, 2, 3, 5, and 7 (every 2 weeks), at Weeks 13, 15, 19, and 25, and then at 12-week intervals while on treatment. A sample at the end of infusion (within 15 minutes) will be collected at Weeks 1, 7, 13, and 25. Samples will be collected at the End-of-Treatment visit and the Safety Follow-up visit.

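### AUC for dose proportionality runs to the last quantifiable sample, so at 1 mg/kg it can cover a shorter time than at higher doses and exaggerate a more than proportional rise

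*SAP*

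**What the plan says.** Dose-escalation SAP 16.5.4 plans boxplots of dose-normalised parameters and scatterplots with regression lines, for AUC0-t, AUC0-∞ and Cmax. Inclusion is limited as follows: "Dose proportionality will be evaluated for avelumab using data from subjects with a full PK profile, and will be presented graphically as follows". The SAP does not say what makes a profile full.

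SAP 16.5.3 defines AUC0-t as "Area under the serum concentration-time curve from time zero to the last quantifiable concentration". The terminal-slope window should span at least twice the resulting half-life. If more than 20% of AUC0-∞ is extrapolated, AUC0-∞ and the parameters derived from it leave the descriptive statistics.

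Protocol 3.3 based its preliminary finding of linearity on Cmax and AUCtau, from "rich serum concentration-time data obtained over a complete dosing interval of 2 weeks". Protocol 8.5.3.2 takes AUC0-t to the last observation by the linear trapezoidal rule. The SAP takes it to the last quantifiable value with linear-up, log-down.

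Protocol 3.4.1 reports: "At dose level 1 mg/kg, 2 out of 3 subjects displayed less than 90% TO at trough serum concentrations". It adds: "Avelumab serum concentrations were below the quantification limit of 0.2 µg/mL in these 2 subjects".

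Protocol 7.5.1 schedules "Day 1: prior to and at the end of the 1-hour infusion, and at 0.5, 1, 2, 4, 6, and 12 hours after infusion". Samples at 24, 36 and 48 h are optional, and the next is before the Day 15 infusion (336 h).

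**The concern.** A dose comparison of AUC needs the same time span at every dose. Here the span depends on concentration, and so on dose. Protocol 3.3 gives median first-dose troughs of 3.7, 20 and 44 µg/mL at 3, 10 and 20 mg/kg, all well above 0.2 µg/mL, so AUC0-t at those doses generally reaches 336 h. A 1 mg/kg subject with an unquantifiable trough contributes 48 h at most, or 12 h if the optional samples were missed.

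The missing area lowers dose-normalised exposure at the lowest dose. That is also where faster, target-mediated elimination would show, so the figures would mix a real difference in clearance with an artefact of where integration stops.

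**Working it through.** **Inputs.** Volume 55 mL/kg (protocol 3.3, the 10 mg/kg mean, assumed to hold at 1 mg/kg). Quantification limit 0.2 µg/mL (protocol 3.4.1). Mean half-lives 69 ± 21 h at 1 mg/kg and 106 ± 29 h at 10 mg/kg (protocol 3.3). Sample times from protocol 7.5.1. Decline is taken as mono-exponential and the 1-hour infusion as a bolus.

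**Reproducing a stated figure.** C(336) = (Dose/V) × 2^(−336/t½). At 10 mg/kg: (10/0.055) × 2^(−336/106) = 20.2 µg/mL, against the stated median of 20. At 3 mg/kg (t½ 84 h) the model gives 3.4 against 3.7. At 20 mg/kg (t½ 134 h) it gives 64 against 44, a poor fit.

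**Half-life implied by a below-limit trough.** At 1 mg/kg, C(0) = 1/0.055 = 18.18 µg/mL. For C(336) < 0.2, t½ must be below 336 × ln 2 / ln(18.18/0.2) = 51.6 h. The lower end of 30 h is an assumption.

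**Area lost.** With k = ln 2/t½, AUC0-T = (18.18/k) × (1 − e^(−kT)). The last two columns put half the limit (0.1 µg/mL) at 336 h and add the log-down area (C48 − 0.1) × 288 / ln(C48/0.1).

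| t½ (h) | AUC0-48 (µg·h/mL) | AUC0-336 (µg·h/mL) | Kept | Lost | AUC0-336 with half the limit | Error |
|---|---|---|---|---|---|---|
| 30 | 527 | 787 | 67% | 33% | 942 | +20% |
| 40 | 593 | 1,046 | 57% | 43% | 1,107 | +6% |
| 51.6 | 643 | 1,340 | 48% | 52% | 1,240 | −7% |

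If the last quantifiable value is at 12 h, the share kept is (1 − 2^(−12/t½)) / (1 − 2^(−336/t½)): 24% at 30 h and 15% at 51.6 h.

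**Effect on the dose comparison.** At 10 mg/kg, AUC0-336/Dose = 106/(ln 2 × 0.055) × (1 − 2^(−336/106)) = 2,472. The ratio to an affected 1 mg/kg subject is:

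- as planned (336 h against 48 h): 2,472/527 = 4.7, 2,472/593 = 4.2 and 2,472/643 = 3.8 at 30, 40 and 51.6 h;
- on a common 336 h: 2,472/787 = 3.1, 2,472/1,046 = 2.4 and 2,472/1,340 = 1.8.

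Truncation multiplies the ratio by about 1.5 to 2.1, but the ratio stays above 1 on the common interval.

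**Whether AUC0-∞ helps.** With the last value at 48 h, the extrapolated share is 2^(−48/t½): 33% at 30 h and 52% at 51.6 h. It reaches 20% or less only for t½ ≤ 48/log₂5 = 20.7 h. The 20% rule would therefore usually remove these subjects' AUC0-∞.

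**The two AUC0-t definitions.** If the unquantifiable trough is set to zero and the protocol's linear rule runs to 336 h, the added triangle is C48 × 288/2. At 40 h this is 7.91 × 144 = 1,140, so AUC = 1,732 against 1,046 (+66%). The range is +77% at 30 h to +51% at 51.6 h, the opposite sign to the SAP's error.

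**The case against.** **The subjects may not enter the figures.** A subject without a quantifiable trough might not have a full profile. This stands: the truncation is conditional on how that term is read. But exclusion would leave one of these three subjects and drop the fast eliminators, so the term needs defining either way.

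**The half-lives do not fit the stated 1 mg/kg value.** A standard deviation of 21 h needs at least two subjects with a half-life, so either more than these three were treated or half-lives were obtained from short profiles. At 69 h the model gives 0.62 µg/mL at 336 h, which is quantifiable. At one standard deviation below, 48 h, it gives 0.14, which is not. The 30 to 52 h range is model-derived and remains unreconciled. The two-of-three figure also comes from a small occupancy subset (n=9 over all doses).

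**The schedule may have been different.** First enrolment was planned for Q1 2013, and Appendix I shows that Day 8 and Day 22 visits were dropped only after Amendment 7 (30 July 2014). The documents do not say whether PK was drawn at Day 8. With a 168 h sample, the model predicts 0.37 to 1.9 µg/mL, which is quantifiable, and the loss falls to about 2% to 10%. This stands.

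**Little depends on the figures.** There is no proportionality test or decision rule, Cmax is untouched, and the planned individual profiles and trough tables would show the below-limit values. This limits the consequence but does not make the AUC comparison like for like.

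**Conclusion.** The point holds in conditional form. AUC0-t as defined does not guarantee a common time span across doses, and the SAP lists no fixed-interval AUC, although the protocol's own linearity statement used one. If subjects with an unquantifiable trough enter the figures and the current schedule applied, their AUC0-t omits roughly 33% to 52% of AUC0-336h. That rests on mono-exponential decline, a volume of 55 mL/kg at 1 mg/kg and half-lives of 30 to 52 h. Target-mediated elimination would change the size.

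Three stronger readings are not supported:

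- A reader might infer that the comparison is certainly biased, with integration ending at 48 h. The full-profile set is undefined, the 48 h sample is optional, and the sampling in force when 1 mg/kg was given is not in the documents.
- A reader might infer that the apparent non-proportionality is an artefact. Mean half-life is shorter at 1 mg/kg (69 h against 106 h), and the modelled ratio stays above 1 on a common interval.
- A reader might infer that AUC0-∞ cannot be calculated for these subjects. The twofold window is worded as a recommendation. The binding rule is the 20% limit, which removes values from descriptive statistics; SAP 16.5.4 does not say whether the plots follow it.

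**What to change.** In dose-escalation SAP 16.5.4:

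1. Base the AUC dose-proportionality figures on AUC0-336h (AUCtau) at every dose, with a stated rule for a below-limit Day 15 value and those subjects flagged in the plots. Half the limit at 336 h is workable; its error is about +20% to −7% over half-lives of 30 to 52 h under the model above.
2. Show AUC0-48h for all doses alongside. It needs no substitution where the 48 h sample exists, but it is less sensitive to differences in elimination: the modelled ratio of 10 to 1 mg/kg is only 1.4 to 1.2.
3. Define the full-profile set and state that a below-limit trough does not remove a subject from it.
4. Keep AUC0-t for listings, and reconcile its end point and trapezoidal rule with protocol 8.5.3.2.

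The cost is SAP wording, one extra partial-AUC setting in the PK software and one substituted value per affected subject. No new sampling is needed.
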